11.2. Local Injection Site Reactions

Local injection site reactions will be listed, and tabulated by treatment group and MedDRA preferred term for comparison of the total number of reactions, type of reaction, severity and time of occurrence (treatment week).

11.3. Clinical Laboratory Evaluations

All laboratory data will be converted to standard units during the Data Management process. The laboratory data will be listed with suitable flags indicating abnormal values (L=Lower than reference range, H=Higher than reference range).

Summary statistics for the laboratory values as well as their changes from baseline at each time will be tabulated for all laboratory parameters.

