During the first four weeks (first 4 infusion cycles from Visit 2 to Visit 3), all infusions will be administered at the study site. Apart from Visit 3, where at least the first session of an infusion cycle will also be administered at the site, the next two weeks can be performed either at the patient's home by the mobile healthcare research nurses or at the site (decision to be taken by Investigator and patient based on previous experience). Thereafter, SCIG infusions will be administered at home by mobile healthcare research nurses, apart from Visits 4-9, where at least the first session of an infusion cycle will be administered at the site. Before starting home treatment, a diary will be provided to the patients for documenting AEs and local tissue reactions at injection sites, body temperature around 1 hour after the end of the infusion, and any changes in concomitant drug and non-drug therapies between visits. The date of home treatments, batch numbers, number of vials, volume and speed of infusion, number and location of injection sites will be recorded by the mobile nurses. Based on the Investigator's decision a home infusion can be replaced with an on-site infusion if considered medically relevant..

 If on day of IMP: before IMP administration;

 Measurements of the vital signs will be carried out before, at least once during, and 1 hour ( $\pm 10$  min) after the end of the infusion session;

 If on day of IMP: at least 1 hour post-infusion (after the second infusion if both sessions are done on site);

 1 hour ( $\pm 10$  min) after the end of the infusion session;

 For patients from GAM10-08 study: GAM10-08 Week 40 Termination Visit will be SCGAM-02 Baseline Visit. GAM10-08 Week 40 test results will be used for SCGAM-02 Baseline Visit evaluations;

 For patients from GAM10-08 study: SCGAM-02 Informed consent to be provided to patient before GAM10-08 Week 40 visit;

 At minimum, all patients should be assessed for vital signs, adverse events and concomitant therapy. Other safety and/or efficacy laboratory assessments, and physical exam should be repeated only if found abnormal at the termination visit;

 Only parameters found abnormal at the termination visit will be re-assessed.

(X) To be performed whenever hemoglobin is found to have decreased by  $\geq 2$  g/dL from baseline.

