#### Before infusion:

- Randomization and enrolment.
- SF-36v2.
- Physical examination.
- Vital signs and body weight.
- Blood sample for safety laboratory (hematology and clinical chemistry).
- Blood sample for additional safety lab parameters (serum haptoglobin and plasma-free hemoglobin)
- Direct Coombs' test (if positive, the antibodies responsible for the positive Coombs' test will be eluted to investigate their specificity (anti-A, anti-B or anti-D)).
- Urinalysis.
- Blood sample for serum IgG.
- Blood samples for enzymes.
- Blood sample for viral markers.
- Blood sample for D-dimers.
- CSM.
- CDASI.
- Visit registration in IRT.

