#### Before the infusion session:

- Patient diary check.
- Physical examination.
- Vital signs.
- Blood sample for safety laboratory (hematology and clinical chemistry). If hemoglobin is found to have decreased by  $\geq 2$  g/dL from baseline, the additional safety laboratory parameters (serum haptoglobin, plasma-free hemoglobin) and Direct Coombs' test will be performed as well.
- Blood sample for serum IgG.
- Blood samples for enzymes.
- CSM.
- CDASI.
- Visit registration in IRT.

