**Before the infusion session:**

- Patient diary check.
- Physical examination.
- Vital signs (including body weight).
- Blood sample for safety laboratory (hematology and clinical chemistry).
- Blood sample for additional safety lab parameters (serum haptoglobin, plasma-free hemoglobin).
- Direct Coombs' test (if positive, the antibodies responsible for the positive Coombs' test will be eluted to investigate their specificity (anti-A, anti-B or anti-D)).
- Urinalysis.
- Blood sample for serum IgG.
- Blood samples for enzymes.
- Blood sample for biomarkers of disease activity.
- CSM.
- CDASI.
- Visit registration in IRT.

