**6.1.10 Termination Visit (Week 32 or Drop-out Visit)**

The Termination Visit is performed at Week 32.

The following assessments will be performed:

- SF-36v2.
- Patient diary check.

- Physical examination.
- Vital signs and body weight.
- Blood sample for safety laboratory (hematology and clinical chemistry).
- Blood sample for additional safety lab parameters (serum haptoglobin, plasma-free hemoglobin).
- Direct Coombs' test (if positive, the antibodies responsible for the positive Coombs' test will be eluted to investigate their specificity (anti-A, anti-B or anti-D)).
- Urinalysis.
- Blood sample for serum IgG.
- Blood samples for enzymes.
- Blood sample for viral markers.
- Blood sample for biomarkers of disease activity.
- CSM.
- CDASI.
- Wells probability score for DVT. If score is likely for DVT ( $\geq 2$  points), perform Doppler scan and take blood sample for D-dimers.
- Wells probability score for PE.
- Monitoring of AEs.
- Assessment of local injection site reactions.
- Documentation of concomitant therapy.
- Pregnancy test (in WOCBP).
- Visit registration in IRT.

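### SAP 11.3 tabulates laboratory means and changes at every time point, including those where only patients with a triggering finding are sampled

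*SAP*

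**What the plan says.** SAP 11.3 gives one rule for the whole laboratory section: "Summary statistics for the laboratory values as well as their changes from baseline at each time will be tabulated for all laboratory parameters". It makes no exception for samples taken only under a condition. It also promises a listing with flags for low and high values.

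The protocol contains three kinds of conditional sampling.

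- **Hemolysis markers.** These are taken in all patients at baseline (Protocol 6.1.2: "Blood sample for additional safety lab parameters (serum haptoglobin and plasma-free hemoglobin"), at Weeks 12 and 24 (6.1.5 and 6.1.8: "Blood sample for additional safety lab parameters (serum haptoglobin, plasma-free hemoglobin") and at the Week 32 or drop-out visit (6.1.10). The direct Coombs' test follows the same schedule. At Weeks 4, 8, 16, 20 and 28 the condition is a hemoglobin fall of at least 2 g/dL from baseline. Only then, says 6.1.3, "the additional safety laboratory parameters (serum haptoglobin, plasma-free hemoglobin) and Direct Coombs' test will be performed as well". The Table 1 footnote agrees: "To be performed whenever hemoglobin is found to have decreased by" that amount.
- **D-dimers.** These are taken in all patients at baseline (6.1.2). Afterwards, only a Wells DVT score of at least 2 leads the site to "perform Doppler scan and take blood sample for D-dimers" (6.1.10, with the same instruction at the other visits).
- **Week 33.** Table 1, footnote 9: "Only parameters found abnormal at the termination visit will be re-assessed". Protocol 6.1.11 says the same for laboratory tests. D-dimers at Week 33 again follow the Wells score.

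Two general SAP rules also bear on this. Section 8 sets the default denominator for percentages at the whole analysis population. Section 8.3 presents the frequency of missing values and plans no analysis of their pattern.

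**The concern.** At the conditional times, a patient enters the table only because of something observed after randomisation. A side-by-side mean of octanorm and placebo patients is then not a comparison of randomised groups, and each subset may hold only a handful of patients.

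This matters most for hemolysis. Hemolytic transfusion reactions are one of the two adverse events of special interest (Protocol 7.3.5). A positive Coombs' test and a fall in haptoglobin below normal are two of the four criteria for suspected intravascular hemolysis (7.3.5.2). A drug effect can change how many patients meet the trigger, how far the marker moves among them, or both. A table of means does not separate these.

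There are two side effects. Under the default denominator, patients never tested for Coombs' at a conditional visit would be counted as not positive. Under the missing-data rule, samples that were never due could be counted as missing.

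At Week 33 the selection is on the parameter's own abnormal value one week before. Part of any apparent recovery is regression to the mean.

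**Working it through.** **1. Schedule against the tabulation rule** (Protocol Table 1 and 6.1.2 to 6.1.11)

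| Parameter | Taken in all patients | Taken only if triggered |
|---|---|---|
| Haptoglobin, plasma-free hemoglobin, Coombs' | Weeks 0, 12, 24, 32/drop-out | Weeks 4, 8, 16, 20, 28 (hemoglobin fall ≥ 2 g/dL); Week 33 (abnormal at termination) |
| D-dimers | Week 0 | All later visits (Wells DVT ≥ 2) |
| Hemoglobin, LDH and other safety laboratory tests | Every visit through Week 32 | Week 33 (abnormal at termination) |

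The hemolysis markers are conditional at 5 of the 8 post-baseline visits through Week 32 and unconditional at 3. The last row rests on the instruction at each visit: "Blood sample for safety laboratory (hematology and clinical chemistry".

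**2. How many patients would be tabulated.** The documents give no trigger rate, so a range is assumed. With 39 patients per arm (SAP 6), the expected number is 39 × p, and the chance of 0 or 1 sample is (1 − p)^39 + 39p(1 − p)^38.

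| Assumed p | Expected per arm | Chance of 0 or 1 |
|---|---|---|
| 2% | 0.8 | 82% |
| 5% | 2.0 | 41% |
| 10% | 3.9 | 9% |
| 20% | 7.8 | 0.2% |

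**3. What selection does to an arm difference.** The documents give no laboratory variances. Two simple models, with every input assumed, bracket the behaviour.

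*Model A: the drug acts on haptoglobin only through hemoglobin.* Hemoglobin change is normal with SD 1.0 g/dL. The mean is 0 on placebo and −0.5 g/dL on octanorm. The correlation r with haptoglobin change is 0.3 or 0.6.
- Mean hemoglobin change among triggered patients: placebo −φ(2)/Φ(−2) = −2.37; octanorm −0.5 − φ(1.5)/Φ(−1.5) = −2.44.
- Triggered haptoglobin mean (r times these): placebo −0.71 or −1.42 SD; octanorm −0.73 or −1.46 SD.
- All-patient arm difference: 0.5r = 0.15 or 0.30 SD. Triggered arm difference: 0.02 or 0.04 SD.
- Triggered patients per visit: 39 × 0.0228 = 0.9 on placebo and 39 × 0.0668 = 2.6 on octanorm.

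The difference almost vanishes from the means and shows in the count.

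*Model B: hemolysis occurs in a subgroup.* Hemolysis affects 10% on octanorm and 1% on placebo. Mean hemoglobin change is −2.2 g/dL with hemolysis and −0.1 g/dL without, with common SD s. Mean haptoglobin change is −0.8 g/L with hemolysis and 0 without.
- All-patient difference: −0.8 × (0.10 − 0.01) = −0.07 g/L.
- Trigger probability: a = Φ(0.2/s) with hemolysis, b = Φ(−1.9/s) without.
- Triggered mean for hemolysis rate h: −0.8 × ha / [ha + (1 − h)b].

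| s (g/dL) | Octanorm | Placebo | Triggered difference (g/L) |
|---|---|---|---|
| 0.5 | −0.80 | −0.79 | −0.01 |
| 0.7 | −0.76 | −0.52 | −0.24 |
| 1.0 | −0.55 | −0.14 | −0.42 |

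Here the same true difference is understated in one setting and exaggerated in two.

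**4. Week 33.** Assume a stable parameter, selected because it was below its 2.5% limit at Week 32. The selected mean is −φ(1.96)/0.025 = −2.34 SD. With visit-to-visit correlation r, the expected move back towards the mean is (1 − r) × 2.34. That is 1.17, 0.70 or 0.23 SD for r = 0.5, 0.7 or 0.9, with no true change.

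**The case against.** The strongest reply is that a harm signal is well covered elsewhere.

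- Hemolysis markers are measured in everyone at baseline and at Weeks 12, 24 and 32. Hemoglobin and LDH are measured in everyone at every visit through Week 32, so the 0.5 g/dL fall in Model A would show, unselected, in the hemoglobin table for the same visit.
- SAP 11.1 reports the incidence and number of hemolytic transfusion reactions and of thromboembolic events, with narratives. The data monitoring committee reviews these events in real time.
- SAP 11.6.2 gives Wells scores, Doppler scans and D-dimers a dedicated listing. SAP 11.3 lists all laboratory values with flags, and the summary tables show the number of non-missing values.
- The list of tables is still to be written, so the layout could be settled there.

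All of this stands, and it limits the point. A reader might infer that hemolysis markers and D-dimers are only ever drawn in patients with an abnormal result, and that the plan could hide an excess of hemolysis on octanorm. The documents support neither inference. The unconditional visits rule out the first, and the Wells DVT score is a clinical score, not a laboratory result. The remaining evidence rules out the second for the trial as a whole. The near-equality of triggered means in Model A also follows from its assumption that the drug reaches haptoglobin only through hemoglobin. Model B removes that assumption, and the bias can then go the other way.

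The reply does not make the conditional-visit means meaningful. A displayed n shows that few patients were sampled. It does not say how many met the trigger out of how many assessed, and it does not correct the Coombs' denominator. Week 33 is openly follow-up of abnormal findings and no claim of recovery is planned, but SAP 11.3 as written still calls for a change-from-baseline table there.

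**Conclusion.** The point holds as a minor correction to safety reporting. Followed literally, SAP 11.3 yields by-arm means and changes in patients selected on post-randomisation findings. This affects the hemolysis markers at five visits, D-dimers at every visit after baseline, and all laboratory tests at Week 33. These tables are not a randomised comparison and can err in either direction.

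The schedule mismatch is read directly from the documents and needs no assumption. Every size given above is illustrative, because the documents supply no trigger rates, laboratory variances or correlations. The direction of the bias in an arm difference depends on the model chosen, so no single figure should be quoted as its size. The primary endpoint, significance level and sample size are unaffected.

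**What to change.** In SAP 11.3:

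- Limit by-visit summary statistics and changes from baseline to visits where the parameter is scheduled in all patients: haptoglobin and plasma-free hemoglobin at Weeks 0, 12, 24 and 32/drop-out, with Coombs' frequencies at the same visits. Summarise D-dimers at baseline only.
- For triggered samples, report by arm (a) the number and percentage of patients meeting the trigger, with all patients assessed for that trigger at that visit as denominator; (b) the number abnormal among those tested; and (c) a listing. For Coombs' frequencies at triggered visits, use patients tested as the denominator.
- For Week 33, report resolved or not resolved among patients abnormal at termination, in place of means.
- State that samples not due under the protocol are not counted as missing.

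The cost is a few sentences in the SAP and matching entries in the table list that is still to come. No new data are needed, and the sampling triggers themselves do not change. The downside is that no mean is shown at the triggered time points.

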11.4. Viral Markers

Virology markers will be assessed at the screening visit and at the (early) termination visit; these data will be listed as well with suitable flags indicating positive results. Furthermore shift tables will be presented to show any changes in the viral status during the study.

11.5. Vital Signs

To evaluate short-term tolerance, monitoring of vital signs including blood pressure, body temperature, pulse and respiratory rate will be performed at all infusion visits. These parameters will be summarized by infusion and measurement time, using the standard set of summary statistics for both, absolute values and changes from baseline, where the baseline value is the pre-infusion measurement.

11.6. Further Safety Evaluations

11.6.1. Physical Examination

A general physical examination will be performed at the screening and baseline visit and all relevant abnormalities will be documented. The physical examination will be repeated at each study visit, including the termination visit (irrespective of whether termination is regular or premature), and any clinically relevant worsening from the status at screening will be documented as an AE.

11.6.2. Wells Scores

To identify all occurrences of DVT and PE, Wells' probability scores will be assessed at all visits. If the DVT score is likely for DVT (≥ 2 points), a Doppler scan is performed, and D-dimers are evaluated. These parameters will be combined into a dedicated listing to facilitate the assessment of these TEAEs of special interest.

12. Reporting Conventions

The following reporting conventions will be adopted for the presentation of study data. These conventions will enhance the review process and help to standardize presentation with common notations.

12.1. General Reporting Conventions

- All tables and data listings will be developed in landscape orientation, unless presented as part of the text in a CSR.
- Figures will in general also be presented in landscape orientation, unless presented as part of the text in a CSR. Exceptions are the Trellis plots that will be presented in portrait orientation.
- Legends will be used for all figures with more than one variable or item displayed.
- Figures will be in black and white, unless color figures have been identified as useful for discriminating presentation in the figure. Lines in figures should be wide enough to view the line after being photocopied.
- Specialized text styles, such as bolding, italics, borders, shading, superscripted and subscripted text will not be used in tables, figures and data listings unless they add significant value to the table, figure, or data listing.
- Only standard keyboard characters should be used in tables and data listings. Special characters, such as non-printable control characters, printer specific, or font specific characters, will not be used on a table, figure, or data listing. Hexadecimal character representations are allowed (e.g., μ , α , β).
- The ICH numbering convention is to be used for all tables, figures and data listings.
- All footnotes will be left justified and placed at the bottom of a page. Footnotes must be present on the page where they are first referenced. Footnotes should be used sparingly and must add value to the table, figure, or data listing. If more than four footnote lines are planned then a cover page may be used to display footnotes.
- Missing values for both numeric and character variables will be presented as blanks in a table or data listing. A zero (0) may be used if appropriate to identify when the frequency of a variable is not observed.
- All date values will be presented as DDMMYYYY (e.g., 29AUG2001) format.
- All observed time values will be presented using a 24-hour clock HH:MM format (e.g. 15:26).
- Time durations will be reported in HH:MM notation. The use of decimal notation to present (display) time durations should be avoided (e.g. 0.083h = 5min) unless it is necessary to show the computation of time differences in a table, figure, or data listing, in which case both notations may be used to display the time duration.
- All tables, figures and data listings will have the name of the program, and a date stamp on the bottom of each output.

12.2. Population Summary Conventions

- Population(s) represented on the tables or data listings will be clearly identified in the title as “Population: <name of population>” where <name of population> is any of the analysis population names or abbreviations defined in section 7 (safety analysis set (SAF), full analysis set (FAS), etc.).

- Sub-population(s) or special population(s) descriptions will provide sufficient detail to ensure comprehension of the population (e.g., FAS Females, Per-Protocol Males >60 years of age) used for analysis in a table or figure.
- Population sizes may be presented for each treatment or dosing category as totals in the column header as (N=xxx), where appropriate.
- Population sizes shown with summary statistics are the samples sizes (n) of subjects with non-missing values.
- All population summaries for continuous variables will include: N, mean, SD, median, Q1, Q3, minimum and maximum.
- All percentages are rounded and reported to a single decimal point (xx.x%).

Property of Octapharma. Do not copy or distribute without written permission.

13. Tables, Listings and Figures

To be supplied in a separate document later when all feedback from authorities will be available.

Property of Octapharma. Do not copy or distribute without written permission.
